4.2 Endpoints

Primary Endpoints:

- The percentages of subjects with, and the frequencies and intensities of solicited local adverse events (AEs) reported on the day of vaccination and the 7 subsequent days (Days 1-8).
- The percentages of subjects with, and the frequencies, intensities and relationship to vaccination, of solicited systemic AEs reported on the day of vaccination and the 7 subsequent days (Days 1-8).
- The duration (in days) of solicited local AE, of solicited systemic AE and of the individual solicited AEs.
- The percentages of subjects with and frequencies and intensities of any unsolicited and related unsolicited AEs reported on the day of vaccination and the 28 subsequent days (Days 1-29).
- The percentages of subjects with and frequencies and relationship to vaccination, of any serious adverse events (SAEs) and any MAAEs up to 12 months post last dose.
- The percentages of subjects with and frequencies and relationship to vaccination of any adverse events of special interest (AESIs) up to 12 months post vaccination.

Secondary Endpoints:

For safety

- The percentages of subjects with and frequencies of SAEs and MAAEs related to study vaccination from 12 months post last dose up to 24 months post last dose (trial end).
- The percentages of subjects with and frequencies and relationship to vaccination of any AESIs from 12 months post last dose up to 24 months post last dose (trial end).

For the characterization of the humoral immune response

- Percentages of subjects with rabies-specific serum VNTs ≥ 0.5 IU/ml by trial group on Days 1 (pre-vaccination), 15, 43, and 12, 18* and 24* months post last dose.
- Serum geometric mean titers (GMTs) of VNTs by trial group on Days 1, 8, 15, 29, 36, 43, 57, 91, and 6 and 12, 18* and 24* months post-last dose.

* Will be performed only in subjects with detectable RABV-G-specific IgG at 6 months after the last vaccination or Day 91 if the Month 6 blood sample is not available.

Exploratory Endpoints:

For the evaluation of the innate immune response:

- Serum cytokine concentrations* including but not limited to CXCL10, CCL3, IL-6, TNF- α and IFN- γ , at pre-vaccination and 4 hours post-vaccination on Day 1, and Days 2 or 3** and 8 after each vaccination.
- Transcriptome profiling* on the day of vaccination at pre-vaccination, and Days 2 or 3** and 8 after each vaccination.

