10.3.7 Missing data

Analysis of vaccination variables will be done on a valid case basis, i.e., for missing observations, no imputation for missing data, such as last observation carried forward (LOCF), will be applied. For safety data, some missing or partially missing variables will be imputed as follows:

- For start date:
 - If the AE start date year value is missing, the date uncertainty is too high to impute a rational date. Therefore, if the AE year value is missing, the imputed AE start date is set to missing.
 - If the AE start date year value is less than the treatment start date year value, the AE started before treatment. Therefore:
 - If the AE year is lower than the treatment year and the AE month is missing, the imputed AE start date is set to the mid-year point (i.e., 01JULYYYY).

- If the AE year is lower than the treatment year and the AE month is not missing, the imputed AE start date is set to the mid-month point (i.e., 15MONYYYY).
- If the AE start date year value is greater than the treatment start date year value, the AE started after treatment. Therefore, if the AE year is greater than the treatment year and the AE month is missing, the imputed AE start date is set to the year start point (i.e., 01JANYYYY).
- For resolution date:
 - If date of resolution is completely missing, it is assumed that it resolved at the date of the end of the AE assessment period.
 - If year is present, it is assumed that it resolved on 31 December of that year (i.e., 31DECYYYY), or at the end of the AE assessment period if earlier.
 - If year and month are present, it is assumed that it resolved on the last day of that month, or at the end of the AE assessment period if earlier.

No other safety variables will be imputed. In case the number of missing/partial dates for solicited local AEs, solicited systemic AEs or individual solicited AEs is higher than expected for the analysis of durations (in days), a sensitivity analysis will be conducted to assess the impact on the primary endpoint.

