6.3 Handling of Dropouts or Missing Data

Summaries will be based on a valid case basis, ie, on observed data only, unless specified otherwise.

Missing or incomplete dates of (unsolicited) AEs will be imputed to assess whether an AE occurred prior to or after the first vaccination dose. Imputed dates are only further used for classification, but no other calculation like durations will be done. Imputation will also be considered for missing or incomplete CMs dates to determine whether a CM is prior, concomitant or ongoing.

The most conservative approach will be systematically considered. If the AE onset date is missing/incomplete, it is assumed to have occurred during the trial vaccination phase (ie, considered a post-vaccination AE) except if the partial onset date or other data, such as the end date, indicate differently.

The following algorithms will be applied to missing and incomplete AE start and stop dates:

Start Dates

- If the day portion of the start date is missing, then the start date will be estimated to be equal to the date of first administration of trial product, provided the start month and year are the same as the administration of trial product and the stop date is either after the first administration of trial product or completely missing. Otherwise, the missing day portion will be estimated as “15.”
- If both the day and month portions of the start date are missing, then the start date will be estimated to be equal to the date of first administration of trial product, provided the start year is the same as the first administration of trial product and the stop date is either after the first administration of trial product or completely missing. Otherwise, if the start year is lower than the year of first administration of the trial product, the event will be assumed to start on the mid-year point of the given year (eg, ??-??-2013 is estimated as 01-JUL-2013).
- If the start year is after the year of first administration of the trial product, the start date will be estimated as the first day of the year (ie, 01-JAN-YYYY).
- If the start date is completely missing and the stop date is either after the first administration of trial product or completely missing, the start date will be estimated to be the day of first administration of trial product. Otherwise, the start date will be estimated to be the first day of the same year as the stop date.

Stop Dates

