11.1 Safety Endpoints and Variables

The analysis of the primary objective to assess the safety and reactogenicity profile will examine solicited and unsolicited adverse events.

The primary endpoints include the following:

- The percentages of subjects with, and the frequencies and intensities of solicited local AEs reported on the day of vaccination and the 7 subsequent days (Days 1-8).
- The percentages of subjects with, and the frequencies, intensities, and relationship to vaccination of solicited systemic AEs reported on the day of vaccination and the 7 subsequent days (Days 1-8).
- The duration (in days) of solicited local AEs, of solicited systemic AEs, and of the individual solicited AEs.
- The percentages of subjects with and frequencies and intensities of any unsolicited and related unsolicited AEs reported on the day of vaccination and the 28 subsequent days (Days 1-29).

- The percentages of subjects with and frequencies and relationship to vaccination of any serious AEs (SAEs) and any medically attended AEs (MAAEs) up to 12 months after the last dose.
- The percentages of subjects with and frequencies and relationship to vaccination of any AEs of special interest (AESIs) up to 12 months after the last dose.

Secondary safety endpoints are:

- The percentages of subjects with and frequencies of SAEs and MAAEs related to study vaccination from 12 months after the last dose up to 24 months after the last dose (trial end).
- The percentages of subjects with and frequencies and relationship to vaccination of any AESIs from 12 months after the last dose up to 24 months after the last dose (trial end).

Further safety variables include the following:

- Extent of exposure
- Physical examination, weight, BMI
- 12-Lead electrocardiogram
- Vital signs
- Safety laboratory - hematology, biochemistry, coagulation
- Laboratory - Urine dipstick pregnancy test, serum pregnancy test (human chorionic gonadotropin)

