Arthralgia	2	Moderate, some interference with normal activity
	3	Significant, prevents normal activity
	0	Absent
Nausea/ Vomiting	1	Mild, no interference with normal activity
	2	Moderate, some interference with normal activity
	3	Significant, prevents normal activity
Diarrhea	0	Absent
	1	2 or 3 loose stools or <400 g/24 hours
	2	4 or 5 stools or 400 – 800 g/24 hours
	3	6 or more watery stools or >800 g/24 hours or requires outpatient i.v. hydration

*United States Food and Drug Administration toxicity grading scale; i.v. = intravenous.

Solicited AEs are also documented as AEs on the respective eCRF pages by the investigator, if they are serious and/or are ongoing on Day 8.

For every solicited AE, the maximum over all grades documented in the diary on the day of vaccination and the 7 subsequent days will be defined as grade (intensity) of this solicited AE.

Frequencies and percentages of local and systemic solicited AEs reported on the day of vaccination and the 7 subsequent days will be displayed by vaccination group, by subject overall and vaccination dose (number).

An overall summary table will display frequencies and percentages by grade (intensity) including any grade of:

- Any solicited AEs
- Local solicited AEs

- Systemic solicited AEs
- Related systemic solicited AEs
- Any solicited AEs ongoing on Day 8

Frequencies and percentages by grade (intensity), including any grade, will also be displayed for the individual terms of solicited AEs. Gradings of zero (AE is absent) will not contribute to the numbers tabulated.

The duration in days of a solicited AE will be represented by the number of days with diary entries of Grade ≥ 1 (out of Days 1-8) reported by a subject per solicited AE term and diary (corresponding to vaccination dose). Thus, the duration in days can range from 1 to 8 per prespecified solicited event term and vaccination dose administered.

The duration of Grade 3 solicited AEs will be derived by counting only days with Grade 3 entries.

For subjects without a specified event term, no duration of this event will be calculated, ie, no zero durations are possible.

The number of days of solicited AEs, as well as the number of days of solicited Grade 3 AEs will be tabulated with basic statistics by vaccination group and vaccination dose (number) for any solicited AE, any local solicited AE, any systemic solicited AE, any related systemic solicited AE, and the individual terms of solicited AEs.

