14.3.1.1.2.1 Number of Days of Local Solicited Adverse Events Post Dose 1, Safety Analysis Set

		CV7202 1 µg (N = xx)	CV7202 2 µg (N = xx)	CV7202 5 µg (N = xx)	Rabipur (N = xx)
Pain	n	xx	xx	xx	xx
	Mean (SD)	xx.x (xx.xx)	xx.x (xx.xx)	xx.x (xx.xx)	xx.x (xx.xx)
	Median	xx.x	xx.x	xx.x	xx.x
	Min, Max	xx, xx	xx, xx	xx, xx	xx, xx
Redness	n	xx	xx	xx	xx
	Mean (SD)	xx.x (xx.xx)	xx.x (xx.xx)	xx.x (xx.xx)	xx.x (xx.xx)
	Median	xx.x	xx.x	xx.x	xx.x
	Min, Max	xx, xx	xx, xx	xx, xx	xx, xx
Swelling	n	xx	xx	xx	xx
	Mean (SD)	xx.x (xx.xx)	xx.x (xx.xx)	xx.x (xx.xx)	xx.x (xx.xx)
	Median	xx.x	xx.x	xx.x	xx.x
	Min, Max	xx, xx	xx, xx	xx, xx	xx, xx
Itching	n	xx	xx	xx	xx
	Mean (SD)	xx.x (xx.xx)	xx.x (xx.xx)	xx.x (xx.xx)	xx.x (xx.xx)
	Median	xx.x	xx.x	xx.x	xx.x
	Min, Max	xx, xx	xx, xx	xx, xx	xx, xx

Table counts solicited adverse events with grade > 0 only.

Duration is calculated as the sum of days with local systemic adverse event (days 1 to 8).

PROGRAM SOURCE: tlfl-##, DATA CUT OFF DATE: DDMMYYYY

RUN DATE: DDMMYYYY hh:mm

Sponsor
Protocol number

Clinical Study Report
Page x of y

14.3.1.1.2.2 Number of Days of Local Solicited Adverse Events Post Dose 2, Safety Analysis Set

		CV7202 2x1 µg (N = xx)	CV7202 2x2 µg (N = xx)	Rabipur (N = xx)
Pain	n	xx	xx	xx
	Mean (SD)	xx.x (xx.xx)	xx.x (xx.xx)	xx.x (xx.xx)
	Median	xx.x	xx.x	xx.x
	Min, Max	xx, xx	xx, xx	xx, xx
Redness	n	xx	xx	xx
	Mean (SD)	xx.x (xx.xx)	xx.x (xx.xx)	xx.x (xx.xx)
	Median	xx.x	xx.x	xx.x
	Min, Max	xx, xx	xx, xx	xx, xx
Swelling	n	xx	xx	xx
	Mean (SD)	xx.x (xx.xx)	xx.x (xx.xx)	xx.x (xx.xx)
	Median	xx.x	xx.x	xx.x
	Min, Max	xx, xx	xx, xx	xx, xx
Itching	n	xx	xx	xx
	Mean (SD)	xx.x (xx.xx)	xx.x (xx.xx)	xx.x (xx.xx)
	Median	xx.x	xx.x	xx.x
	Min, Max	xx, xx	xx, xx	xx, xx

Table counts solicited adverse events with grade > 0 only.

Duration is calculated as the sum of days with local systemic adverse event (days 1 to 8).

PROGRAM SOURCE: tlfl-##, DATA CUT OFF DATE: DDMMYYYY

RUN DATE: DDMMYYYY hh:mm

CureVac AG
CV-7202-104

Statistical Analysis Plan
24 February 2022

Sponsor
Protocol number

Clinical Study Report
Page x of y

14.3.1.1.2.3 Number of Days of Local Solicited Adverse Events Post Dose 3, Safety Analysis Set

Rabipur			
(N = xx)			
Pain	n	xx	
	Mean (SD)	xx.x (xx.xx)	
	Median	xx.x	
	Min, Max	xx, xx	
Redness	n	xx	
	Mean (SD)	xx.x (xx.xx)	
	Median	xx.x	
	Min, Max	xx, xx	
Swelling	n	xx	
	Mean (SD)	xx.x (xx.xx)	
	Median	xx.x	
	Min, Max	xx, xx	
Itching	n	xx	
	Mean (SD)	xx.x (xx.xx)	
	Median	xx.x	
	Min, Max	xx, xx	

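### The primary endpoint duration of solicited AEs counts only diary Days 1–8, so any reaction continuing past Day 8 is understated, which lowers the mean and maximum

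*SAP*

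**What the plan says.** Protocol 4.2 lists as a primary endpoint: "The duration (in days) of solicited local AE, of solicited systemic AE and of the individual solicited AEs". SAP 11.1 repeats it: "The duration (in days) of solicited local AEs, of solicited systemic AEs, and of the individual solicited AEs". In both lists the two solicited-AE endpoints just before it are restricted to Days 1–8. The duration endpoint is not.

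SAP 11.2.1 supplies the derivation. Per term and per vaccination dose, duration is "represented by the number of days with diary entries of Grade ≥ 1 (out of Days 1-8"), with the consequence: "Thus, the duration in days can range from 1 to 8 per prespecified solicited event term and vaccination dose administered". The footnote to table shell 14.3.1.1.2.1 says the same: "Duration is calculated as the sum of days with local systemic adverse event (days 1 to 8").

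SAP 11.2.1 also has the investigator document solicited AEs on the AE pages of the eCRF "if they are serious and/or are ongoing on Day 8". The shell for listing 16.2.7.1.1, which shows AE eCRF entries, has start and end date columns. Protocol Appendix 11 has AEs followed until the outcome is known or nothing more can be learned. SAP Appendix A gives the standard duration as date2 − date1 + 1.

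Protocol 10.3.7 says that if the number of missing or partial dates for solicited AEs "is higher than expected for the analysis of durations (in days), a sensitivity analysis will be conducted". SAP section 12 declares one change to the protocol analyses, the dropped per-protocol sets, and does not mention duration.

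**The concern.** A count limited to eight diary days cannot tell a reaction that ended on Day 8 from one that lasted three weeks. The information needed to separate them appears to be collected, because events still present on Day 8 move to the AE pages, but no SAP rule carries the end date back into the duration.

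This is a first-in-human trial with reactogenicity in its primary objective, and protocol 5.7 says that reactogenicity at 5 µg contributed to lowering the later doses. The rare long reaction is what a duration endpoint should reveal. In the planned tables it would appear as a value of 8 or less, with nothing to show that it was cut off.

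**Working it through.** **Inputs.** The diary covers the day of vaccination and the 7 following days (SAP 11.2.1). The day-count rule is in SAP 11.2.1 and the date formula in SAP Appendix A. The documents give no end dates, so the last day of the event, E, is an assumption and is varied below.

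**Reproducing the plan's range.** 1 + 7 = 8 diary days, so a subject with the event has a count from 1 to 8. This agrees with the SAP.

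**Formulas.** For an event present every day from onset day d to last day E (Day 1 = vaccination):

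- SAP duration = min(E, 8) − d + 1
- Date-based duration = E − d + 1
- Shortfall = max(0, E − 8)
- Largest value the SAP can report for onset on day d = 8 − d + 1 = 9 − d

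| Onset d | Last day E | SAP | Date-based | Shortfall |
|---|---|---|---|---|
| 1 | 8 | 8 | 8 | 0 |
| 1 | 10 | 8 | 10 | 2 |
| 1 | 15 | 8 | 15 | 7 |
| 1 | 29 | 8 | 29 | 21 |
| 7 | 15 | 2 | 9 | 7 |
| 8 | 15 | 1 | 8 | 7 |

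Events that end on or before Day 8 without gaps are unaffected. A late-onset event is cut to well under 8 days: onset on Day 7 can never give more than 2.

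**Effect on a group summary (assumed data).** Take ten subjects with the event, nine with 2 days and one running from Day 1 to E.

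- SAP mean: (9×2 + 8)/10 = 2.6
- E = 10: (18 + 10)/10 = 2.8
- E = 15: (18 + 15)/10 = 3.3
- E = 29: (18 + 29)/10 = 4.7

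The maximum is 8 under the SAP against 10, 15 or 29. The median is 2 in every case. With three long events of ten and E = 15, the means are (7×2 + 3×8)/10 = 3.8 and (7×2 + 3×15)/10 = 5.9, and the median is still 2. The shortfall in the mean is the sum of (E − 8) over truncated events, divided by the number of subjects with the event.

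**Grade 3 durations.** These are counted from diary days in the same way and have the same limit.

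**The case against.** The strongest defence is that the count matches the collection window and is openly labelled. Solicited AEs are collected only for eight days, the tables are titled as numbers of days, and the footnote gives the range. Events ongoing on Day 8 are not hidden: they are summarised by grade, flagged in the solicited-AE listings, and visible in the daily tables. Protocol 5.8.1 expects reactions typically to resolve within 24 hours, so few may be affected. All of this stands. It does not remove the truncation, because the ongoing counts and flags carry no duration and the duration tables do not mark which values were cut.

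A reader might infer that the protocol fixed an uncapped, date-based duration which the SAP then reversed. The documents do not support that. The protocol gives no derivation and leaves the definition of analysis variables to the SAP (10.3.1). Its rules for missing or partial resolution dates stop at the end of the AE assessment period, and its sensitivity analysis is conditional. What remains is that protocol 10.3.7 speaks of dates of solicited AEs in the duration analysis and the SAP does not say what became of this.

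It is also tempting to cite SAP 6.3, "Imputed dates are only further used for classification, but no other calculation like durations will be done", as barring date-based durations here. That paragraph concerns dates of unsolicited AEs.

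A blank diary day adds nothing to the count, but the daily tables keep a separate row for days not assessed. It is therefore too strong to say that the plan reports blank days as event-free. The duration rule is simply silent on them.

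Finally, no sentence states outright that an end date is recorded for solicited AEs ongoing on Day 8. This is inferred from their entry on the AE pages, the date columns in a listing titled for unsolicited AEs, and the follow-up rule. The annotated eCRF would settle it.

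**Conclusion.** The point holds. Every solicited AE that continues past Day 8 is understated by E − 8 days, with an effective cap of 9 minus the onset day. The mean and maximum are biased downward. The median is little affected while such events are few.

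The number of events affected cannot be determined from the documents, and the group examples rest on assumed end days. A reader might infer that differences between dose levels are compressed. That would follow only if long reactions were more common or longer at some doses, and the documents contain nothing to show this. The analysis is descriptive, so no test or error rate is at stake. What is at stake is an accurate description of a primary endpoint, using data that the documents indicate are already collected.

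**What to change.** - Keep the diary count, but label it as days with Grade 1 or higher within Days 1–8. Use the same label for the Grade 3 count.
- For events ongoing on Day 8, add a duration from onset to the AE-page end date, using date2 − date1 + 1.
- Flag unresolved events as censored. Do not give them a duration to last contact, which could put values near two years into the range.
- Report the number of truncated events per group in the duration tables.
- Attribute Rabipur Dose 1 events ongoing on Day 8 to Dose 1 and flag their overlap with the Dose 2 diary, which starts that day.
- Record in SAP section 12 that this replaces the conditional duration sensitivity analysis of protocol 10.3.7.

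The cost is one extra derivation linking the diary to the AE page. The drawback is that a calendar span can include gap days, so it is a slightly different measure from counted diary days. The two should be shown side by side under separate labels.

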11.2.2 Unsolicited Adverse Events

Serious AEs, intercurrent medical conditions, AEs leading to trial or vaccine withdrawal, AEs of special interest (AESIs) and MAAEs will be collected by the investigator in the eCRF throughout the trial.

AEs with a suspected potential immune-mediated disease etiology will be considered AESIs. The investigator will assess if an AE is an AESI. A list of AESIs is provided in Appendix 10 of the protocol.

AEs that are reported as related to the test vaccine will be considered trial vaccine-related; missing classifications concerning trial vaccine relationship will also be considered trial vaccine-related.

Every unsolicited AE will be assigned to a vaccination dose (number) by consideration of the period of 28 days after vaccination administration. Unsolicited AEs can be assigned to either day 1 to 28 (dose 1 for any vaccination group), or day 29 to 57 (dose 2 for 2-dose regimens or dose 3 for the Rabipur group). For the Rabipur group, vaccination dose 2 is administered 8 days after vaccination dose 1, therefore no assignment of unsolicited AEs to vaccination dose 2 is done for the Rabipur group.

All AE summaries will be restricted to those AEs that occurred after the first administration of the trial product. Any other AE (ie, AE starting after trial entry and before the first vaccination) will be reflected only in the data listings. If it cannot be determined whether the AE occurred after the first administration of the trial product due to a partial onset date, then it will be counted as such. Verbatim terms in the eCRFs will be mapped to preferred terms (PTs) and system organ classes (SOCs) using the Medical Dictionary for Regulatory Activities (version 21.0 or higher).

The occurrence of unsolicited AEs reported on the day of vaccination and the 28 subsequent days will be presented. In addition selected AE summary tables will be repeated for unsolicited AEs occurring at any time after the first administration of the trial product.

Each AE summary will be displayed by vaccination group and dose regimen. Summaries by vaccination dose (number) will also be provided for all AEs. Summaries that are displayed by SOC and PT will be ordered by descending order of incidence of SOC and PT within each system organ class. Summaries will display number and percentage of subjects with at least 1 event and the number of events by vaccination group.

Summaries of the following types will be presented:

- Overall summary of unsolicited AEs that contain an overview of each item below
- All AEs
 - Mild (grade 1) AEs
 - Moderate (grade 2) AEs
 - Severe (grade 3) AEs
- Related AEs
 - Mild (grade 1) related AEs
 - Moderate (grade 2) related AEs
 - Severe (grade 3) related AEs
- SAEs
- Related SAEs
- MAAEs
- AEs leading to withdrawal from study
- AEs leading to discontinued vaccination

- AESIs

Laboratory data will be graded by the site in the AE form according to the United States Food and Drug Administration toxicity grading scale and the Common Terminology Criteria for Adverse Events Version 5.0.

